POPULATION - INCLUSION CRITERIA:	
The MHRA have requested that no age range is defined in order to capture all data on Ayendi use. Hence data from patients dosed outside the SmPC restrictions will be collected also to provide a comprehensive review of use in clinical practice. Thus any patient who has been prescribed Ayendi as part of routine treatment in the ED is eligible for the study.
 
To be eligible for inclusion into this study the subjects must fulfil all of the following criteria:

	
 1. Patient has been administered Ayendi Nasal Spray by the attending ED Healthcare Professional as part of ED treatment. 2. Parent(s)/legal guardian/adult patient (whichever is applicable) must be able and willing to provide written informed consent before the patient is discharged from the ED. 3. Where applicable, child patients should assent to allow their data to be used for the study.
POPULATION - EXCLUSION CRITERIA:	None
VARIABLES:	
Primary Parameters:
 
 ▶ Rate (%) of doses given (mg/kg) which deviate from the posology as written in the SmPC. ▶ Patients with previous opioid usage immediately prior to Ayendi (%) 
Secondary Parameters:
 
 ▶ Time of administration (including pre-arrival at hospital, if appropriate) ▶ Dose Prescribed (mg/kg) vs Dose Given (mg/kg) ▶ Product strength and Number of sprays given ▶ Diagnosis for which Ayendi was prescribed (% used for off- label indications) ▶ Participating ED practice setting (%) ▶ Administrator (%) ▶ Concomitant medication ▶ Patient demographics (including patients who do not fit within the categories defined in the SmPC). ▶ Adverse events (%)

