8.1 Primary objective

To determine the rates of:

- ▶ Doses given (mg/kg) which deviate from the posology as written in the SmPC.
- ▶ Previous opioid usage immediately prior to Ayendi (%)

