9.1.1 Study Methods

This is purely an observational study. The attending physician will provide routine standard of care and prescribe medicinal products as per hospital standard of care and the patient's requirements – **this is not part of the study.**

In order to provide the potential of obtaining the broadest cohort, consent will be taken **after** the patient has been given the Ayendi Nasal Spray as part of routine clinical practice.

After Ayendi has been administered but before the patient is discharged from the ED, approved hospital staff (including the direct clinical care team and hospital research nurses) will approach the adult patient/parent(s)/legal guardian/patient (whichever is applicable) to discuss the use of the patient's data for research purposes. If the adult patient/parent(s)/legal guardian(s)/patient (whichever is applicable) agrees to the inclusion of the patient's data in the study, approved hospital staff will transcribe the required data from the ED records onto study specific Case Report Forms. Data not recorded as routine practice on the ED records and patient notes should not be recorded on the CRF, even if the information is available.

The **study period** is defined as the time after the patient was administered Ayendi until they are discharged from the ED. After the patient has been treated in the ED, they may be discharged or transferred to a hospital ward. There will be no follow-up information recorded once the patient has been discharged from the ED.

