9.4 Variables and Data Sources

All clinical data to be collected for the study will be transcribed from the ED records onto study specific CRFs by approved hospital staff.

Clinical data which are not recorded routinely in the ED records as part of clinical practice should not be included in the CRF, even if the information is available.

Information transcribed directly from the ED records (where available):

- ▶ Demographic data: weight, age, gender
- ▶ Indication (site and nature of injury/trauma) / diagnosis
- ▶ Relevant current and ongoing medical history
- ▶ Concomitant medications taken during the study period
- ▶ Details (name, position, qualifications, whether training to use Ayendi nasal spray has been undertaken) regarding the Ayendi administrator
- ▶ Time of dose
- ▶ Strength and dose of Ayendi prescribed
- ▶ Strength and dose administered
- ▶ Any issues with dosing
- ▶ Adverse events that occur prior to discharge/transfer from the ED
- ▶ Serious Adverse Events that occur prior to discharge/transfer from the ED

Study-specific information from the informed consent form and the study identification log includes the following:

- ▶ Unique subject identifier to identify site and subject number in study
- ▶ Administration setting
- ▶ Date of informed consent (subject assent, if applicable)
- ▶ Confirmation of adherence to inclusion criteria

In addition to individual Case Record Forms, the following information will be collected by the Clinical Research Associate at each site as part of the site initiation and routine monitoring visits:

- ▶ How Ayendi is generally prescribed
- ▶ How Ayendi is routinely administered
- ▶ How Ayendi administration is recorded in the controlled drug logs
- ▶ Steps taken by the site to minimise dosing error

This is purely an observational study and no further information will be documented as part of the study.

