9.5 Study size

The study will aim to recruit a minimum of 400 patients who attend the hospital emergency department and are administered Ayendi Nasal Spray.

The sample size has been powered to accurately estimate both the rate of incorrect dosing and use in association with other opioids.

The rate of incorrect dosing and concomitant opioid use are based on the previous DIASAFE study (DIA002). In that study 14 of 226 subjects (6%) received the incorrect dose and 5 of 226 subjects (2%) received concomitant opioids defined as any other opioids (including any given if Ayendi/diamorphine is insufficient treatment) received from the time of the injury until the subject's discharge from the ED.

Regardless of event rate, 400 subjects will provide a maximum half-width of the 95% confidence interval (based on a normal approximation) of 4.9%. With this sample size, the half-width of the 95% confidence interval for the incorrect dosage rate is 2.3% and for the opioid usage rate is 1.4%. Thus a sample size of 400 subjects provides precise estimates for a range of rates.

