5.4 Is exposure classified based on biological mechanism of action?				
5.5 Does the protocol specify whether a dose-dependent or duration-dependent response is measured?				

Comments:

--

Section 6: Endpoint definition and measurement	Yes	No	N/A	Page Number(s)
6.1 Does the protocol describe how the endpoints are defined and measured?				16(section9.4)
6.2 Does the protocol discuss the validity of endpoint measurement? (e.g. precision, accuracy, sensitivity, specificity, positive predictive value, prospective or retrospective ascertainment, use of validation sub-study)				See comment

Comments:

Objectives page 12 (section 8), Variables measures page 16 (section 9.4). Summary data from a retrospective observational study of unconsented patients, with no personally identifiable details will be used, to provide validation for these results.

Section 7: Biases and Effect modifiers	Yes	No	N/A	Page Number(s)
7.1 Does the protocol address:				
7.1.1 Selection biases?				21(section9.9)
7.1.2 Information biases? (e.g. anticipated direction and magnitude of such biases, validation sub-study, use of validation and external data, analytical methods)				21(section9.9)
7.2 Does the protocol address known confounders? (e.g. collection of data on known confounders, methods of controlling for known confounders)				

Section 7: Biases and Effect modifiers	Yes	No	N/A	Page Number(s)
7.3 Does the protocol address known effect modifiers? (e.g. collection of data on known effect modifiers, anticipated direction of effect)				21(section9.9)
7.4 Does the protocol address other limitations?				21(section9.9)

Comments:

Prior use of opioids is a primary endpoint
--

Section 8: Analysis plan	Yes	No	N/A	Page Number(s)

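### One primary endpoint is opioid use before Ayendi, but the protocol's only listed medication item starts after Ayendi is given

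*Protocol*

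**What the plan says.** Section 8.1 gives two primary rates, and the second is "Previous opioid usage immediately prior to Ayendi". The abstract lists the same parameter as "Patients with previous opioid usage immediately prior to Ayendi". Section 9.7 names it among the analyses the SAP must describe. The comment under Section 7 of the Annex 2 checklist repeats it: "Prior use of opioids is a primary endpoint".

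Section 9.4 lists what is transcribed from the ED records. Its single medication item is "Concomitant medications taken during the study period", and the abstract's data list has the same item. Study period is a defined term: Section 9.1.1 says it "is defined as the time after the patient was administered Ayendi until they are discharged from the ED". Section 9.4 ends with "This is purely an observational study and no further information will be documented as part of the study".

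Two other places bear on the window. The Study Duration row of the abstract asks for data on the one ED attendance and does not say that collection starts at Ayendi. Section 9.5 describes the opioid use counted in DIA002 as use "received from the time of the injury until the subject's discharge from the ED".

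**The concern.** The endpoint looks back from the Ayendi dose, while the medication item looks forward from it. If the list is followed as worded, a drug given before Ayendi is not transcribed, and a SAP cannot analyse what was never transcribed. Section 9.7 requires SAP approval only before database lock, so the gap could surface after collection has ended.

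Opioid co-medication is a named safety reason for this MHRA-requested study (Section 7), and the sample size is justified partly on opioid use (Section 9.5). Section 9.9.1 adds that consent may depend on whether other opioids were given, so this variable is also needed to judge consent bias. If sites read the window differently, differences between hospitals, which the abstract's objectives set out to evaluate, would partly reflect how the data list was read.

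**Working it through.** **1. The windows side by side**

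- Endpoint (8.1, abstract, 9.7): before the Ayendi dose.
- Medication item (9.4 and abstract, using the 9.1.1 definition): after the Ayendi dose to ED discharge.
- Abstract, Study Duration: the whole ED attendance.
- Planning rate (9.5): injury to ED discharge.

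The first two do not overlap. The third includes time in the ED before Ayendi but not time before arrival. The fourth covers both sides of the dose, but it describes how DIA002 counted opioids and is not a collection instruction for this study.

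**2. Whether another listed item fills the gap**

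The other clinical items in 9.4 are demographics, indication, medical history, administrator details, Ayendi dose and time, dosing issues, and adverse events. The nearest is "Relevant current and ongoing medical history", which is not a drug record and is not timed against the Ayendi dose. The site-level items collected by the monitor concern Ayendi practice only.

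**3. The plan's own precision figures**

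The half-width is 1.96 × √(p(1 − p)/400).

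- p = 0.50: 4.90% (stated 4.9%).
- p = 0.06: 2.33% (stated 2.3%).
- p = 0.02: 1.96 × √(0.02 × 0.98/400) = 1.37% (stated 1.4%).

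All three reproduce, so the sample-size arithmetic is not in question.

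**4. How many patients could be affected**

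The planning rate is 5/226 = 2.21%. The protocol does not say what share s of those uses came before Ayendi, so s is an assumption. The prior-opioid rate is s × 5/226, and the expected count is 400 times that.

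- s = 25%: 0.55%, 2.2 patients.
- s = 50%: 1.11%, 4.4 patients.
- s = 75%: 1.66%, 6.6 patients.
- s = 100%: 2.21%, 8.8 patients.

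The range is about 2 to 9 of 400 patients, all outside the stated window.

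**5. Direction of the error**

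Suppose a fraction c of true prior users is captured and the rest are counted as non-users. The expected reported rate is then c times the true rate, which never exceeds it. If the rest are set to missing instead, there is no such bias from miscounting, but the rate is not estimable where nothing was captured. With complete loss, the shortfall equals the rates in step 4, 0.55 to 2.21 percentage points. The stated 1.4% half-width reflects sampling error and does not allow for this.

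**The case against.** The strongest reply is that the protocol names prior opioid use as a primary endpoint several times, and nothing tells sites to leave earlier opioids out. The Study Duration row supports collection over the whole attendance. The sentence closing the list can be read as barring non-routine data, because the abstract follows it with a sentence about information not recorded in routine practice. The CRF is not shown and may have a prior-medication field.

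Much of this stands. It means that a complete absence of prior-opioid data is one possible outcome and not the only one; uneven capture between sites is as plausible. It does not remove the contradiction. The abstract and 9.1.1 give different windows, and the data list uses the term that 9.1.1 defines narrowly. A CRF field for earlier opioids would itself depart from the list.

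A reader might infer two stronger conclusions that the documents do not support:

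- **That the study would report 0 of 400.** This assumes full literal compliance and that uncollected data are counted as no use. Section 9.7.2 leaves missing-data handling to the SAP.
- **That 8 prior users (2% of 400) are expected and would be lost.** The 2% includes opioids given after Ayendi when it was insufficient, so it is not a prior-use rate.

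**Conclusion.** The point holds as a contradiction in the protocol text that affects a primary endpoint and should be fixed. The data listed in 9.4 and the abstract, read with the 9.1.1 definition, do not include opioid use before Ayendi. The likely result is inconsistent or absent capture, giving a rate that is missing or too low.

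The size is uncertain. About 2 to 9 of 400 patients would lie outside the stated window, on two assumptions: that the DIA002 rate carries over to this study, and that 25% to 100% of those opioid uses preceded Ayendi. The protocol gives no figure for that share. Nothing is claimed about the CRF itself.

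**What to change.** - In Section 9.4 and the abstract's data list, extend the medication item to opioids given before the first Ayendi dose, with drug and time, as routinely recorded in the ED record and including any pre-hospital entries found there.
- State the look-back that counts for the primary endpoint, for example from injury to the first Ayendi dose, and use the same definition in 8.1 and the abstract.
- Keep concomitant medication after Ayendi as a separate item.
- Reconcile the Study Duration row of the abstract with 8.1, 9.1.1 and 9.4, so that one collection window is stated for medication.
- Check that the CRF matches the revised list.

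The cost is slightly more transcription per patient, with no extra patients or procedures. Opioids given before arrival and not noted in the ED record will still be missed, and Section 9.9 should state this as a limitation. If the change is made after the protocol has been approved, defining the look-back may count as a substantial amendment under Section 2, and Section 10 requires MHRA approval for those.

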9.5 Study size

The study will aim to recruit a minimum of 400 patients who attend the hospital emergency department and are administered Ayendi Nasal Spray.

The sample size has been powered to accurately estimate both the rate of incorrect dosing and use in association with other opioids.

The rate of incorrect dosing and concomitant opioid use are based on the previous DIASAFE study (DIA002). In that study 14 of 226 subjects (6%) received the incorrect dose and 5 of 226 subjects (2%) received concomitant opioids defined as any other opioids (including any given if Ayendi/diamorphine is insufficient treatment) received from the time of the injury until the subject's discharge from the ED.

Regardless of event rate, 400 subjects will provide a maximum half-width of the 95% confidence interval (based on a normal approximation) of 4.9%. With this sample size, the half-width of the 95% confidence interval for the incorrect dosage rate is 2.3% and for the opioid usage rate is 1.4%. Thus a sample size of 400 subjects provides precise estimates for a range of rates.

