9.7 Data Analysis

A statistical analysis plan (SAP) will be developed by a qualified statistician and analysis will be performed according to this document. The SAP will specifically include details of how all: Analysis Populations, Demographic and Baseline Characteristics, Completion and Discontinuation information, Medication details and All Analyses (rate of incorrect dosing, rate of previous opioid usage immediately prior to Ayendi, time of dosing, product strength and number of sprays, indication, ED practice setting, administrator, concomitant medication, and adverse events) will be classified and described. The SAP will be reviewed and approved prior to database lock.

The sample size chosen for the study is considered appropriate based on previous experience. This is an observational study of patients receiving prescribed Ayendi in a UK Hospital Emergency Department. The sample size will have sufficient power to estimate both the rate of incorrect dosing and use in association with other opioids.

Changes in the conduct of the study or planned analyses will be reported in the corresponding section of the study report.

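### The 2% rate and 1.4% half-width given for opioid use describe any opioid from injury to ED discharge, not the primary endpoint of opioid use immediately before Ayendi

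*Protocol*

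**What the plan says.** The second primary objective in section 8.1 is "Previous opioid usage immediately prior to Ayendi". The abstract lists the same quantity as a primary parameter, "Patients with previous opioid usage immediately prior to Ayendi". Section 9.7 names it among the analyses that the SAP will describe, and a comment in the ENCePP checklist (Annex 2, section 7) confirms that prior opioid use is a primary endpoint.

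The sizing text uses another quantity. Section 9.5 takes a rate of 2% (5/226) from DIA002, counting those who "received concomitant opioids defined as any other opioids (including any given if Ayendi/diamorphine is insufficient treatment) received from the time of the injury"; the window closes at ED discharge. The study-size entry of the abstract says the same. Both then give a half-width of 1.4% for the opioid usage rate with 400 patients, and the ENCePP checklist (Annex 2, comment under section 3) repeats the 1.4%. Section 9.7 adds: "The sample size will have sufficient power to estimate both the rate of incorrect dosing and use in association with other opioids".

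Section 9.5 also gives a figure that does not depend on the rate: "400 subjects will provide a maximum half-width of the 95% confidence interval (based on a normal approximation) of 4.9"%.

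On data collection, section 9.4 lists concomitant medications for the study period only. Section 9.1.1 defines that period as running from after Ayendi administration to ED discharge.

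**The concern.** The two opioid definitions cover different windows. The sizing definition runs from injury to ED discharge and expressly includes opioids given because diamorphine was not enough, which necessarily come after it. The primary endpoint stops at the Ayendi dose. Nothing in the protocol gives a DIA002 rate for opioids before dosing, or links one definition to the other.

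At stake is the stated precision of one of two primary estimates in a study that the regulator asked for, partly because of co-medication with other opioids. A reader of section 9.5 would take ±1.4% as the planned precision for the primary opioid endpoint, and the protocol offers no basis for that.

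The data-item wording adds a third window. Taken literally, the medication item starts after Ayendi and so does not clearly capture the opioids that the primary endpoint counts.

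**Working it through.** **Inputs.** From section 9.5: n = 400 ("The study will aim to recruit a minimum of 400 patients"), a 95% interval by normal approximation, 14/226 (6%) incorrect doses and 5/226 (2%) any-opioid use. The rate of opioid use before Ayendi is not given, so it is treated below as an assumption and shown over a range.

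**Formula.** Half-width = 1.96 × √(p(1 − p)/400).

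**The protocol's own figures.**
- Maximum, p = 0.5: 1.96 × √(0.25/400) = 4.90% (stated 4.9%).
- Incorrect dose, p = 0.06: 2.33% (stated 2.3%; the unrounded 14/226 gives 2.36%).
- Any opioid, p = 0.02: 1.96 × √(0.0196/400) = 1.37%; p = 5/226 = 2.21%: 1.44% (stated 1.4%).

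All three are reproduced. The fault lies in the quantity to which the 1.4% is attached.

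**Prior-use endpoint, if DIA002 is the guide.** Assume that the window immediately before Ayendi lies between injury and discharge. Prior use is then a subset of any use, so between 0 and 5 of the 226 subjects had it:

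| Prior opioid users in DIA002 | Rate | Half-width, n = 400 |
|---|---|---|
| 1/226 | 0.44% | 0.65% |
| 2/226 | 0.88% | 0.92% |
| 3/226 | 1.33% | 1.12% |
| 4/226 | 1.77% | 1.29% |
| 5/226 | 2.21% | 1.44% |

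At 0/226 the formula degenerates to zero.

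**Prior-use endpoint over a wider assumed range.**

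| Assumed rate | Expected cases in 400 | Half-width |
|---|---|---|
| 0.5% | 2 | 0.69% |
| 1% | 4 | 0.98% |
| 5% | 20 | 2.14% |
| 10% | 40 | 2.94% |
| any | – | at most 4.9% |

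**Normal approximation at low rates.** With 2 of 400 (0.5%) the formula gives 0.5 − 0.69 = −0.19% as the lower limit, which is impossible. The exact (Clopper-Pearson) 95% interval is 0.06% to 1.79%. With 4 of 400 the exact interval is 0.27% to 2.54%, and with 0 of 400 its upper limit is 0.92%.

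**The case against.** The case for leaving the text alone has four parts.

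1. The 4.9% maximum is stated in the same paragraph and applies to any proportion, including prior use. This stands: the study does have a valid precision statement for the endpoint. It says little, though, about an event expected near 2%.
2. Within DIA002, prior use is a subset of any use, so on those data 1.4% is an upper bound on the half-width and not an optimistic figure. This also stands, given the assumption about the window. It does not carry over automatically to DIA003, which sets no age limits and has no exclusion criteria. If opioid use is more common in routine practice, however, the any-opioid rate would rise too. The 5% and 10% rows therefore reflect doubt about transferring the DIA002 rate and do not follow from the mismatch alone.
3. Opioids given after Ayendi are not lost. Concomitant medication is a secondary objective, collected up to discharge and tabulated. A reader might infer that the co-medication question in the rationale goes unanswered, and the protocol does not support that.
4. A reader might infer that the prior-use rate will be set against DIA002's 2% and look favourable only because its window is narrower. No such comparison is planned: reporting is descriptive, and DIA002 is used only for sizing.

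These points limit the consequence. They do not turn the 2% and 1.4% into figures for the named endpoint.

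**Conclusion.** The mismatch is real and stands in the protocol's own text. The 1.4% is correctly calculated for any opioid from injury to discharge, and it is presented as the precision for opioid use in a study whose primary opioid endpoint is use immediately before Ayendi. For that endpoint the half-width is unknown: about 0.65% to 1.44% if 1 to 5 of the 226 DIA002 subjects had prior opioids, 2.1% to 2.9% at assumed rates of 5% to 10%, and never above 4.9%. At rates near 0.5% the normal approximation should not be used.

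Two stronger conclusions are tempting and not supported. One is that 400 patients are too few; no calculation here shows that. The other is that the primary endpoint must be replaced by the sizing definition. The choice of endpoint should determine the sizing text, and section 2 counts a change of primary objective as a substantial amendment, which section 10 makes subject to MHRA approval.

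This should be corrected, but it does not block the study.

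**What to change.** Keep the primary endpoint as it is and correct the text around it.

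- In section 9.5 and the abstract, label the 2% and 1.4% as any other opioid from injury to ED discharge. Label the 1.4% in the ENCePP comment in the same way.
- In the same places, give the prior-use endpoint its own statement: the DIA002 rate of opioids before dosing with its half-width, if that rate is available. Otherwise give half-widths over an assumed range (0.5% ±0.7, 1% ±1.0, 5% ±2.1, 10% ±2.9; maximum 4.9), with exact intervals at the low end.
- In section 9.7, make the sentence on what the sample size can estimate name the quantity it refers to.
- In section 9.4 and the matching abstract list, reword the medication item so that opioids recorded in the ED notes before Ayendi are clearly collected. This stays within the protocol's rule that only routinely recorded data are transcribed.

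The cost is a text edit and a check that the CRF has a field for opioids before Ayendi. The number of patients does not change. The sponsor should check whether the section 9.4 wording meets the protocol's definition of a substantial amendment.

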OBJECTIVES:	
The following information will be collected and evaluated:
 
 ▶ Administration setting ▶ Patient characteristics ▶ Dose administered (to evaluate deviations from the prescribing and dosing instructions in the approved Summary of Product Characteristics) ▶ How prescribed and administered, (to evaluate if there are any differences in drug utilisation between the hospitals and prescribers) ▶ Adverse events ▶ Concomitant medication 
The study will assess patterns of drug utilisation with respect to aspects that may have an impact on its safety (e.g. co-medication [including other opioids], medication errors) and evaluate the effectiveness of risk minimisation activities.

STUDY DESIGN:	
Observational Model: Case-Only
 
Time Perspective: Prospective.

STUDY SIZE:	
A minimum of 400 patients will be recruited from EDs across a minimum of 20 hospitals (from a wide variety with respect to teaching and non-teaching hospitals, geographical coverage across the UK, department size, experience with diamorphine, and combined or separate paediatric EDs). Each site will aim to recruit a minimum of 10 patients and will be limited to a maximum of 60 patients.
 
The sample size will have sufficient power to estimate both the rate of incorrect dosing and use in association with other opioids
 
The rates of incorrect dosing and concomitant opioid use are based on the previous DIASAFE study (DIA002). In that study 14 of 226 subjects (6%) received the incorrect dose and 5 of 226 subjects (2%) received concomitant opioids defined as any other opioids (including any given if Ayendi/diamorphine is insufficient treatment) received from the time of the injury until the subject's discharge from the ED. Regardless of event rate, 400 patients will provide a maximum half-width of the 95% confidence interval (based on a normal approximation) of 4.9%. With this sample size, the half-width of the 95% confidence interval for the incorrect dosage rate is 2.3% and for the opioid usage rate is 1.4%. Thus a sample size of 400 patients provides precise estimates for a range of rates.

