9.2 Study Setting

A minimum of 20 sites across the UK will be included; they will be selected to ensure stratification for teaching and non-teaching hospitals, geographical coverage, department size, experience with diamorphine, and combined or separate paediatric EDs.

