9.7.2 Statistical analysis

Analysis Populations

Data will be presented for the Safety population, that is, it will include all patients for whom appropriate informed consent was obtained to allow collection of their data.

Data Analysis

Statistical analyses will be performed after all patient data have been collected, protocol deviations reviewed, populations have been agreed and the database has been locked.

Details of all analyses will be included in the SAP.

Continuous variables will be summarised using descriptive statistics; n, mean, standard deviation, median, minimum and maximum, while categorical variables will be summarised as the number (and percentage) of patients in each category.

Demographic data will be summarised overall and by weight in accordance with the approved posology categories, and otherwise, as appropriate.

Concomitant medications will be tabulated by weight group along with the current available WHO drug dictionary coding by primary term and generic drug name.

Safety analyses will be simply summarised.

Adverse events will be coded according to the current version of MedDRA.

Missing, Unused or Spurious Data

The handling of missing, unused and spurious data will be described in the SAP.

Deviations from the Planned Statistical Analyses

Any changes to the planned analysis (as described in the protocol and SAP) will be documented in the statistical and clinical study reports.

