9.9 Limitations of the Research Methods

As this is an observation study of post authorisation drug utilisation, the sites included in this study are limited to EDs which have independently, without reference to this study, made the decision to use Ayendi.

In an effort to avoid bias, sites will be included that have a history of the use of nasal diamorphine as well as sites that have rarely or never administered it prior to purchasing Ayendi. Additionally, units that have a dedicated paediatric ED department as well as those that are part of the general adult ED will be included. Also, recruitment per site will be limited to a maximum of 60 patients (15% of the overall sample size) to ensure that the overall estimate is not too affected by one site. By use of these measures, and having a patient population of 400, bias will be reduced, and a representative position of the UK EDs should be obtained.

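### The half-widths of 4.9%, 2.3% and 1.4% assume no correlation between patients of the same ED, so 4.9% is not a maximum and the stated precision is probably optimistic

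*Protocol*

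**What the plan says.** Section 9.5 sets the size: "The study will aim to recruit a minimum of 400 patients who attend the hospital emergency department and are administered Ayendi Nasal Spray". The planning rates come from the earlier safety study: "In that study 14 of 226 subjects (6%) received the incorrect dose and 5 of 226 subjects (2%) received concomitant opioids". The precision claim follows: "Regardless of event rate, 400 subjects will provide a maximum half-width of the 95% confidence interval (based on a normal approximation) of 4.9" per cent. The abstract adds that "the half-width of the 95% confidence interval for the incorrect dosage rate is 2.3% and for the opioid usage rate is 1.4" per cent. The same three figures appear in the comment under Section 3 of the ENCePP checklist (Annex 2). None of these places mentions a design effect, an ICC or clustering by site.

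On sites, Section 9.2 says "A minimum of 20 sites across the UK will be included", and the abstract gives a target of at least 10 and a cap of 60 patients per site. Section 9.9 gives the cap as a guard against one site swaying the result: "recruitment per site will be limited to a maximum of 60 patients (15% of the overall sample size"). The same section mixes EDs with and without a history of nasal diamorphine, and expects the result to represent UK EDs. The abstract lists among its objectives "to evaluate if there are any differences in drug utilisation between the hospitals and prescribers". Section 9.4 has the monitor record how each site prescribes and administers the product and what it does to limit dosing error.

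**The concern.** The precision statement is the only quantitative basis for 400 patients. It is calculated as if they were a simple random sample, whereas they come in groups from EDs that may differ in how they prescribe, dose and train. The protocol allows for such differences in its objectives, site selection and recruitment cap, but not in its precision figures. Patients who share a site then carry less information about UK EDs than the same number drawn independently.

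Both primary outcomes are rates, and the study was requested by the regulator. If the planned widths are too narrow, a reader will expect the dosing-error and opioid rates to be pinned down more tightly than the design may allow.

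**Working it through.** **Inputs from the protocol.** n = 400 (9.5); planning rates 6% and 2% (9.5); 95% level with normal approximation (9.5); at least 20 sites (9.2); 10 to 60 patients per site (abstract).

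**Input assumed.** ICC 0.01 to 0.05; the protocol gives none.

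**Step 1: reproduce the stated figures.** Half-width = 1.96 × √(p(1 − p)/400).

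- p = 0.50: 1.96 × √(0.25/400) = 4.90%
- p = 0.06: 1.96 × √(0.0564/400) = 2.33%
- p = 0.02: 1.96 × √(0.0196/400) = 1.37%

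All three agree with the protocol after rounding. The formula contains no design effect, so independence within site is the unstated assumption. The worst case over event rates is indeed p = 0.50, so 4.9% is a maximum over event rates, but only under that assumption.

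**Step 2: design effect.** DE = 1 + (m* − 1) × ICC, where m* = Σm²/Σm over sites.

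- 20 sites of 20: m* = 20
- 4 sites of 60 plus 16 of 10 (total 400): m* = (4 × 3,600 + 16 × 100)/400 = 16,000/400 = 40
- 40 sites of 10: m* = 10

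All three layouts respect the minimum of 20 sites and the limits of 10 and 60.

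**Step 3: adjusted half-widths.** Multiply the figures of step 1 by √DE.

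| Layout | ICC | DE | Effective n | p = 50% | p = 6% | p = 2% |
|---|---|---|---|---|---|---|
| Any | 0 | 1.00 | 400 | 4.90% | 2.33% | 1.37% |
| 20 × 20 | 0.01 | 1.19 | 336 | 5.35% | 2.54% | 1.50% |
| 20 × 20 | 0.05 | 1.95 | 205 | 6.84% | 3.25% | 1.92% |
| 4 × 60 + 16 × 10 | 0.01 | 1.39 | 288 | 5.78% | 2.74% | 1.62% |
| 4 × 60 + 16 × 10 | 0.05 | 2.95 | 136 | 8.42% | 4.00% | 2.36% |
| 40 × 10 | 0.05 | 1.45 | 276 | 5.90% | 2.80% | 1.65% |

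**Step 4: what the assumed ICC means.** The between-site standard deviation of the true rate is √(ICC × p(1 − p)).

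- At 6%: √(0.01 × 0.0564) = 2.4 points for ICC 0.01, and √(0.05 × 0.0564) = 5.3 points for 0.05.
- At 2%: √(0.01 × 0.0196) = 1.4 points for ICC 0.01, and √(0.05 × 0.0196) = 3.1 points for 0.05.

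The upper end is therefore a demanding assumption, above all for the 2% rate, where the spread exceeds the mean.

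**Step 5: low rates, apart from clustering.** At 2% the study expects 8 events. The exact interval for 8/400 runs from 0.9% to 3.9%, so its upper arm is 3.9 − 2.0 = 1.9 points against the stated 1.4.

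**The case against.** The arithmetic in 9.5 is right under its assumption, and the shortfall rests wholly on an ICC that the protocol does not give. At ICC 0.01 with equal sites, 2.33% becomes 2.54% and 1.37% becomes 1.50%, which matters little in a descriptive study with no planned test. Both 400 and 20 are minima, and more sites reduce the loss, as the 40 × 10 row shows. The cap of 60 limits it too. All of this stands, and it bounds the size of the point. It does not make 4.9% a maximum.

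A reader might infer more than the documents support:

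- *That the study fails to deliver its intervals.* This cannot be stated as fact without a known ICC. At the 6% planning rate the half-width passes 4.9% only at an ICC of about 0.18 (20 × 20) or 0.09 (the uneven layout).
- *That the loss could be far larger.* ICC 0.10 with the uneven layout gives 10.85% at p = 50%. That combines a skewed layout, an event rate far from planning and an extreme ICC: at a 2% rate, 0.10 implies a between-site standard deviation of √(0.10 × 0.0196) = 4.4 points, more than twice the mean.
- *That the normal approximation is badly off.* Its coverage is 89.5% at exactly 2%, but that is a dip caused by discreteness. At 5/226 it is 93.3%.
- *That the protocol plans to report no interval, or an invalid one.* Section 9.7.2 says that "categorical variables will be summarised as the number (and percentage) of patients in each category", but it leaves the details of all analyses to the SAP, which is not at hand. The normal approximation in 9.5 describes planning width only.
- *That dosing is known to be driven by department habit.* The protocol asks whether hospitals differ; it does not say that they do.

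One could also argue that clustering is irrelevant if only the participating sites are of interest. Section 9.9 aims at UK EDs in general, so that defence is not open here.

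**Conclusion.** The point holds as a correction to a stated figure. The three half-widths are simple binomial values. Calling 4.9% a maximum is true only if there is no within-site correlation, and the protocol's own design and objectives leave room for such correlation. The stated precision is therefore probably optimistic.

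Over the assumed ICC range of 0.01 to 0.05 and the two 20-site layouts, the half-width at 6% is about 9% to 72% larger than under independence (2.54/2.33 = 1.09; 4.00/2.33 = 1.72). A SAP that uses a cluster-adjusted interval would correct coverage but would not restore the stated widths.

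The matter should be corrected, but it does not threaten the design. No decision threshold depends on the widths, and 400 patients remains a defensible size.

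**What to change.** In Section 9.5, the abstract and the ENCePP comment, either remove the words that present 4.9% as a maximum whatever the event rate, or say that the three figures assume independence between patients of the same site. In either case add the adjusted half-widths, naming both the ICC range and the site layout, since neither range can be checked without them. For example:

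*Allowing for clustering by ED with an assumed ICC of 0.01 to 0.05, 20 sites of 20 patients give 95% half-widths of 5.35 to 6.84% at a rate of 50%, 2.54 to 3.25% at 6% and 1.50 to 1.92% at 2%. With 4 sites of 60 and 16 of 10, the ranges are 5.78 to 8.42%, 2.74 to 4.00% and 1.62 to 2.36%.*

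Any 95% interval reported for the two primary rates should allow for clustering by site and suit low rates, for example a Wilson interval on the effective sample size. The SAP is a proper place for that detail.

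The cost is a less favourable stated precision and edits in three places. No extra patients or sites are needed, and study conduct does not change.
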